6.2.4. Incidence of adverse events, safety laboratory tests, vital signs and ECG abnormalities

Analysis of adverse events, laboratory abnormalities, vital signs and ECG abnormalities will use the Safety Analysis Set defined in Section 4.

6.2.4.1. Adverse Events

Adverse events (Tier 1, 2 and 3 AEs as described in Section 3.2.4.1) will be summarized by treatment group (including ponsegromab combined) and overall, in accordance with sponsor reporting standards. The adverse events will be sorted in descending frequency within a system organ class. If applicable, subject discontinuations due to adverse events will be detailed and summarized.

Incidence and severity of TEAE and TESAE tables will additionally be produced ('All causality' and 'Treatment related', separately) to summarise the total number of adverse events by preferred term, which will be reported by treatment group (including ponsegromab combined) and overall.

TEAEs classed as Tier 2 events will each be tabulated by treatment group (including ponsegromab combined). The number and percentage of participants will be presented, along with the risk difference (and 95% confidence interval) between each dose of ponsegromab and placebo. No adjustment for multiplicity will be used.

Tier 2 TEAEs will also be presented graphically in two-panel plots; the left panel will present the proportions of TEAEs observed in a dose group of (including ponsegromab combined) and separately placebo, while the right panel will display the 95% confidence interval for the risk differences for each TEAE. A vertical line corresponding to the value of 0 will be added to the right-hand plot. Each panel will be paged by dose of ponsegromab.

Tier 2 TEAE outputs will be ordered in descending point estimate of risk difference within System Organ Class. If two or more events have the same frequency, they will be sorted alphabetically by preferred term. Footnotes will be included on the tables to provide proper interpretation of confidence intervals and to describe how the comparison was conducted, e.g. "Confidence intervals are not adjusted for multiplicity and should be used for screening purposes only. 95% Confidence intervals are provided to help gauge the precision of the estimates for Risk Difference. Risk Difference is computed as ponsegromab versus placebo."

It should be recognized that most studies are not designed to reliably demonstrate a causal relationship between the use of a pharmaceutical product and an adverse event or a group of adverse events. Except for select events in unique situations, studies do not employ formal adjudication procedures for the purpose of event classification. As such, safety analysis is generally considered as an exploratory analysis and its purpose is to generate hypotheses for further investigation. The 3-tier approach facilitates this exploratory analysis.

TEAEs classed as Tier 1 events will be tabulated by treatment group (including ponsegromab combined). Note that Tier 1 events are not planned to be presented graphically due to the small number of expected events.

Injection site reactions (ISR) will also be summarized by treatment group (including ponsegromab combined) and overall, in accordance with sponsor reporting standards. The ISRs will be sorted in descending frequency within a system organ class. Incidence and severity of ISR tables will additionally be produced ('All causality' and 'Treatment related', separately) to summarize the total number of ISR by preferred term, which will be reported by treatment group (including ponsegromab combined) and overall.

Potential immunogenic AEs will be summarized by medical evaluation category and treatment groups (including ponsegromab combined) and overall. The number and percentage of participants, judged to have met the immune reaction criteria (injection site reactions, potential cases of angioedema, anaphylaxis, hypersensitivity, delayed hypersensitivity reactions and events potentially meeting the Sampson criteria), will be tabulated by treatment group (and with ponsegromab treatment groups combined only) and overall, and by severity.

6.2.4.2. Laboratory Data

Laboratory data will be listed and summarized by treatment group (including ponsegromab combined) and overall, in accordance with the sponsor reporting standards.

6.2.4.3. Vital Signs

Absolute values and changes from baseline in supine systolic and diastolic BP, and pulse rate will be summarized by treatment group (including ponsegromab combined) and overall, and timepoint, according to sponsor reporting standards. Tables will be paged by parameter.

In addition, changes from baseline will be analyzed using an MMRM model, as described in Section 5.2.3. The MMRM model will be fitted to the change from baseline at all post-treatment timepoints up to Week 12 using the safety analysis set (as defined in Section 4). Additional terms will be fitted in the model (eg, type of therapy [ie, platinum or not], type of cancer), as appropriate.

Maximum decrease from baseline for supine systolic and diastolic blood pressures and maximum increase from baseline for supine pulse rate will be summarized by treatment group (including ponsegromab combined) and overall, according to sponsor reporting standards.

Maximum absolute values and changes from baseline for supine vital signs will also be summarized descriptively by treatment group (including ponsegromab combined) and overall, using categories as defined in Appendix 6. Numbers and percentages of participants meeting the categorical criteria will be provided. All planned and unplanned post dose time points will be counted in these categorical summaries. All values meeting the criteria of potential clinical concern will be listed.

6.2.4.4. ECGs

Absolute values and changes from baseline for the ECG parameters (ie, HR, PR interval, QT interval, QTcF and QRS complex) will be summarized by treatment group (including ponsegromab combined) and overall, and timepoint according to sponsor reporting standards. Tables will be paged by parameter.

In addition, changes from baseline will be analyzed using an MMRM model, as described in Section 5.2.3. The MMRM model will be fitted to the change from baseline at all post-treatment timepoints up to Week 12 using the safety analysis set (as defined in Section 4). Additional terms will be fitted in the model (eg, type of therapy [ie, platinum or not], type of cancer), as appropriate.

Maximum increase from baseline for QTcF will be summarized by treatment group (including ponsegromab combined) and overall, according to sponsor reporting standards.

Maximum absolute values and changes from baseline for QTcF, PR and QRS will also be summarized descriptively by treatment group (including ponsegromab combined) and overall, using categories as defined in Appendix 6. Numbers and percentages of participants meeting the categorical criteria will be provided. All planned and unplanned postdose timepoints will be counted in these categorical summaries. All values meeting the criteria of potential clinical concern will be listed.

Listings of participants with any single post dose value > 500 msec will also be produced for QTcF.

6.3. Other Safety Summaries and Analyses Endpoint(s)

See Section 6.2.4.

6.4. Other Endpoints/Exploratory Endpoints

6.4.1. Change from baseline in additional physical activity and gait endpoints measured with remote digital sensors at Week 12

Absolute values and changes from baseline in the additional physical activity and gait endpoints (listed in Section 3.4.1) will be summarized descriptively by treatment group and timepoint, as described in Section 5.2.1.

6.4.2. Change from baseline in additional FAACT total and sub-scale scores at Week 12

Absolute values and changes from baseline in the additional FAACT total and sub-scale scores (listed in Section 3.4.2) will be summarized descriptively by treatment group and timepoint, as described in Section 5.2.1.

6.4.3. Serum unbound and total concentrations of ponsegromab on Day 1, Weeks 4, 5, 8, 10, 12 and 16 (follow-up), plus Week 9 and 11 in PK substudy only

PK analyses will be performed using the PK analysis set, as defined in Section 4.

A listing of serum unbound and total concentrations, sorted by treatment group, participant and timepoint, will be produced. The listing will also include the actual times and will include all participants and all timepoints.

Additionally, the following presentations for serum unbound and total concentrations of ponsegromab will be produced, separately for 1) all participants (excluding Week 9 and 11 timepoints) and 2) for only participants in the PK substudy (including all timepoints):

- A summary of concentrations by treatment group and timepoint, where the set of statistics will include n, arithmetic mean, SD, coefficient of variation (CV%), minimum, Q1, median, Q3, maximum, geometric mean, geometric CV%, and the number of concentrations above the LLQ
- Median concentration-time plot (on a semi-log scale, all treatments on the same plot), Q1 and Q3 may be included
- Mean (±SD) concentration-time plot (on a semi-log scale, all treatments on the same plot)
- Median trough concentration-time plot (on a linear scale, all treatments on the same plot), Q1 and Q3 may be included
- Mean (±SD) trough concentration-time plot (on a linear scale, all treatments on the same plot).

Note that the separate presentations for the participants in the PK substudy may be reported in a supplemental CSR rather than the main CSR.

6.4.4. Serum unbound and total concentrations of GDF-15 on Day 1, Weeks 4, 5, 8, 10, 12 and 16 (follow-up), plus Week 9 and 11 in PK substudy only

PD analyses will be performed using the PD analysis set, as defined in Section 4.

A listing of unbound and total GDF-15 serum concentration levels, sorted by treatment group, participant and timepoint, will be produced. The listing will also include the fold change from baseline and will include all participants and all timepoints. For unbound GDF-15, the listing will also include a column to indicate whether the absolute GDF-15 concentration is below the healthy volunteer median level or not.

Additionally, the following presentations for unbound and total GDF-15 serum concentration levels will be produced, separately for 1) all participants (excluding Week 9 and 11 timepoints) and 2) for only participants in the PK substudy (including all timepoints):

- A summary of concentrations (absolute values and fold changes from baseline) by treatment group and timepoint, where the set of statistics will include (as data permit) n, arithmetic mean, SD, CV%, minimum, Q1, median, Q3, maximum, geometric mean, geometric CV% and the number of concentrations above the LLQ
- A summary of whether the absolute unbound GDF-15 concentrations are below the healthy volunteer median level or not, by treatment group and timepoint, as described in Section 5.2.2
- Median concentration-time plots (for absolute values only) (on a linear scale, all treatments on the same plot), Q1 and Q3 may be included
- Mean (±SD, if appropriate) concentration-time plots (for absolute values only) (on a linear scale, all treatments on the same plot).

In all presentations, the fold changes will be presented as percent change from baseline ([fold change from baseline -1]*100).

Note that the separate presentations for the participants in the PK substudy may be reported in a supplemental CSR rather than the main CSR.

6.4.5. Incidence of ADA and NAb

Immunogenicity analyses will be performed on the immunogenicity analysis set defined in Section 4.

If applicable and data permit, immunogenicity analyses will include:

- A listing of ADA and NAb results for all participants
- A summary (both table and figure, if appropriate) of the overall incidence of ADA and NAb
- The percentage of participants who are ADA and NAb positive at each timepoint and the cumulative percentage of ADA-positive or NAb-positive participants up to each timepoint.

If appropriate (e.g. the number of ADA-positive participants is ≥3 per treatment group), the additional analyses below may be performed:

- A spaghetti plot of individual participant ADA and NAb titer over time
- A summary of ADA and NAb titer by time

- Analysis of unbound and total ponsegromab concentration by ADA and NAb status.
 This may include summary tables and box and/or spaghetti plots of concentration data by ADA and NAb status
- Analysis of unbound and/or total ponsegromab concentration by maximum ADA and NAb titer tertile, which may include summary tables and box plots of concentration data by titer tertile if a large number of ADA-positive participants is reported (e.g n>10)
- Analysis of unbound and/or total GDF-15 concentration (as data permit) by ADA and NAb status, which may include summary tables and box and/or spaghetti plots of concentration data by ADA and NAb status
- Analysis of unbound and/or total GDF-15 concentration (as data permit) by maximum ADA and NAb titer tertile, which may include summary tables and box plots of concentration data by titer tertile if a large number of ADA-positive participants is reported (e.g n>10)
- An individual plot of unbound and total ponsegromab concentration, unbound and/or total GDF-15 concentration (as data permit), ADA and NAb titer in ADA-positive participants.

6.4.6. Change from baseline score for PROMIS-Fatigue at Week 12

PROMIS Fatigue T-score will be summarized and analyzed in a similar way to the secondary endpoint described in Section 6.2.1.

6.4.7. Change from baseline score for PROMIS-Physical Function at Week 12

PROMIS Physical Function T-score will be summarized and analyzed in a similar way to the secondary endpoint described in Section 6.2.1.

6.4.8. PGI-C at Week 12; Change from baseline in PGI-S at Week 12

Absolute values in PGI-C will be summarized descriptively by treatment group and timepoint as described in Section 5.2.2.

Absolute values and changes from baseline in PGI-S will be summarized descriptively by treatment group and timepoint as described in Section 5.2.2.

6.4.9. Tumor status according to RECIST 1.1 guidelines using CT scan at Week 12

The overall tumor response will be summarized by treatment, as described in Section 5.2.2, using the categories defined in Appendix 11 of the protocol.

6.4.10. Change from baseline in LSMI derived from CT scans at Week 12; Percent change from baseline in skeletal muscle and adipose tissue measures derived from CT scans at Week 12

Absolute values and changes from baseline in LSMI will be summarized descriptively by treatment group and timepoint, as described in Section 5.2.1.

Change from baseline in LSMI will be analyzed using ANCOVA as described in Section 5.2.5. Additional terms for type of therapy [i.e. platinum or not] and type of cancer will be fitted in the model.

Absolute values and percent changes from baseline in skeletal muscle and adipose tissue measures (listed in Section 3.4.10) will be summarized descriptively by treatment group and timepoint, as described in Section 5.2.1.

6.4.11. Change from baseline albumin and pre-albumin levels at Week 12

Absolute values and fold changes from baseline in albumin and pre-albumin will be summarized descriptively by treatment group and timepoint, as described in Section 5.2.1.

6.4.12. Survival status at end of Part A

Survival status at the end of Part A (Week 12) will be summarized descriptively by treatment group and overall, as described in Section 5.2.2.

Time to death will be summarized descriptively by treatment group, as described in Section 5.2.1. A cumulative incidence plot, as described in Section 5.2.6 will also be produced. Time to death will be analyzed using a Cox-proportional hazards model, as described in Section 5.2.7. All deaths will additionally be listed.

6.4.13. Response as defined by a ≥3.5% increase from baseline in body weight at Week 12

Response as defined by a ≥3.5% increase from baseline in body weight will be summarized descriptively by treatment group and timepoint, as described in Section 5.2.2, with no imputation for missing data, including all post-baseline timepoints up to Week 12 (ie. Weeks 4, 8 and 12). Barcharts of the percentages over time will also be produced, with all treatments on the same plot.

The percentage of responses (and 90% CIs) at Week 12 will also be reported by treatment after multiple imputation for missing values as per Section 5.3.1. These responses will also be analyzed separately using a logistic regression model (as described in Section 5.2.8), where missing values will be imputed using multiple imputation as per Section 5.3.1. The logistic regression model will be fitted to the data at Week 12 only.

6.5. Subset Analyses

Additional analyses will be performed on the primary endpoint (change from baseline body weight) to assess the effect of the following two subgroup factors:

- Type of cancer (i.e. NSCLC, PANC or CRC)
- Type of therapy (ie, platinum or not) at randomization [+/- 28 days]
- Screening Roche GDF-15 (dichotomized using < or ≥ overall study median level (or an alternative cut-point, if appropriate))

These analyses will be performed on the censored analysis set, as defined in Section 4.

For each subgroup factor, absolute values, changes from baseline and percent changes from baseline in body weight will be summarized descriptively by subgroup factor, treatment group and timepoint, as described in Section 5.2.1. Tables will include baseline and all post-baseline timepoints.

For each subgroup factor, change from baseline in body weight will be analyzed using an MMRM model, as described in Section 6.1.1.1. Additional terms for the subgroup factor and its interaction with treatment group, time and the treatment-by-time interaction, will be included in the model. Other terms (eg, type of therapy [i.e. platinum or not] and type of cancer; described in Section 6.1.1.1) will be dropped from the model, as appropriate. LS means (and 90% CIs) and mean differences versus placebo (and 90% CIs) will be provided. The p-values for the subgroup interaction terms will be included in the tables, e.g. as a footnote. No adjustments will be made for multiplicity.

If the MMRM model cannot be fitted to the data, or the model is deemed inappropriate, the model may be simplified, or the analysis may not be performed.

Additionally, screening Roche GDF-15 will be plotted vs Week 12 change from baseline body weight using a scatterplot. The plot will include all participants and may be colored/trellised by different cancer types and/or type of therapy.

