# 2.2. Background

At the present time, treatments for cancer related cachexia are limited. Pharmacologic interventions associated with improvements in appetite improvement or body weight gain include progesterone analogues and corticosteroids. The ASCO, in its 2020 *Management of Cachexia Guidelines*, stated that there is no recommended pharmacologic standard of care for patients with cancer associated cachexia.

One of the biomarkers associated with cancer cachexia is the cytokine GDF-15. GDF-15, also known as MIC-1, is a member of the TGFb superfamily. In healthy individuals the major source of circulating GDF-15 is believed to be the liver, although it is also expressed by the kidneys, lung and adipose tissue. GDF-15 is secreted by tumor cells and is associated with cachexia in cancer patients.

In addition, published clinical data and internal animal model data suggest that administration of platinum therapy can induce increases in serum GDF-15 concentrations. Clinical literature and internal animal model data also suggest that the nausea, emesis and anorexia observed with platinum therapy may be mediated, at least in part, by platinum-induced elevations in GDF-15.

Therefore, it is hypothesized that cachexia in many types of cancer, including NSCLC, PANC, and CRC, is largely mediated via GDF-15 and that suppression of GDF-15 in these patients may lead to improvement in serious aspects of cachexia such as anorexia leading to unintended weight loss, fatigue and impaired mobility. Furthermore, given the observations of GDF-15 elevation with platinum therapy, patients receiving standard of care antitumor treatment that includes systemic platinum- based therapy, may be a specific population that could potentially gather additional- benefit from GDF-15 inhibition.

Ponsegromab is an anti-GDF-15 mAb that is currently being investigated in study participants with cancer who have elevated concentrations of GDF-15 and cachexia. The objective of this clinical study is to determine if ponsegromab administered at three different doses every 4-weeks over 12-weeks can reduce the study participants' cachexia related symptom burden and improve their quality of life compared to placebo during 12-weeks of treatment.

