#### 4.3. Justification for Dose

In the part A of this study, ponsegromab will be administered with 100, 200, or 400 mg Q4W SC for a total of 3 doses. The proposed doses were determined based on all relevant information obtained from nonclinical safety studies and clinical data (including safety, tolerability, PK and PD) available. These clinical data included data from 2 completed studies in healthy participants (C3651001 and C3651002, see IB), clinical data (including safety, tolerability, PK, and PD) from the phase 1b study in cancer cachexia patients (C3651009), and the expected duration of GDF-15 suppression, defined as the time it suppress GDF-15 to below the median observed in healthy subjects (0.71 ng/mL).

The median baseline GDF-15 in NSCLC, PANC, and CRC patients are expected to be approximately 3.02, 3.32, and 3.50 ng/mL, respectively, and the 95th percentile are expected to be 8.69, 9.35, and 13.4 ng/mL, respectively. It is assumed that the composition of the cancer types will be similar to that observed in study C3651009, which is 4:4:3 for NSCLC, CRC, and PANC, respectively. Based on preliminary population PK/PD simulations, the proposed 100 mg Q4W SC dose is expected to suppress the unbound GDF-15 concentration in ~64%, and ~28% of the assumed cancer cachexia patients for 2, and 4 weeks, respectively. The proposed 200 mg Q4W SC dose is expected to suppress the unbound GDF-15 concentration in ~92%, and ~72% of the cancer cachexia patients for 2, and 4 weeks, respectively. The proposed high dose of 400 mg Q4W SC dose is expected to suppress the unbound GDF-15 concentration in >90% of the cancer cachexia patients for 4 weeks.

Based on these preliminary PK/PD simulations, the predicted steady state total ponsegromab Cmax, AUCtau, and Cavg, following 100, 200, and 400 mg Q4W SC doses, along with the corresponding safety margins calculated using exposure data from the 6-month toxicology study in monkeys (See IB), and exposure multiples calculated using total exposure data following a single 300 mg SC dose to healthy participants in study C3651001 are summarized in Table 3. The corresponding steady state unbound ponsegromab exposures and exposure multiples calculated using unbound exposure data from study C3651001, are summarized in Table 4.

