#### **Disease Characteristics:**

- 2. Documented histologic or cytologic active diagnosis of NSCLC, PANC, or CRC and are currently receiving, or have completed, SOC treatment for this cancer (which may include systemic therapy).
- 3. Cachexia defined by Fearon criteria of weight loss as (See Section 8.1.1 for details if the participant's body weight is unavailable from medical record):
  - BMI <20 kg/m^2 with involuntary weight loss of >2% within 6 months prior to Screening;

or

- involuntary weight loss of >5% within 6 months prior to screening irrespective of BMI.
- Serum GDF-15 concentrations of ≥1.5 ng/mL (as measured using the Investigational Use Only Roche Elecsys GDF 15 assay) at Screening.
- 5. Participants who are assessed by the investigator to have:
  - an ECOG PS ≤3, and,
  - a life expectancy of at least 4 months to be able to complete Part A.

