## 8.7.1. GDF-15

Blood samples of approximately 6 mL, to provide a minimum of 2 mL serum, will be collected for measurement of serum concentrations of total and unbound GDF-15 at time points specified in the SoA. The GDF-15 sample collection at the Week 5 visit is considered an optional sample. It will not be considered a protocol deviation if the participant is unable to make this visit. In addition, if a participant has an unplanned site visit for any reason, (chemotherapy, radiology, other doctor appointments, etc.), a GDF-15 sample may be collected, if feasible, provided the total volume taken during the study does not exceed 550 mL during any period of 56 consecutive days.

At the Screening visit, two GDF-15 samples will be collected (6-mL for each). One GDF-15 (Roche) sample will be analyzed using the IUO Roche Elecsys GDF-15 assay, for determination of enrollment eligibility. In addition, this sample may be used to help support development of a potential companion diagnostic test for ponsegromab. This screening assay will be validated in a CLIA accredited central laboratory. The second Screening GDF-15 (Pfizer) sample, as well as the GDF-15 samples collected at the other time points specified in the SoA, will be analyzed for unbound and total GDF-15 using validated Pfizer assays in compliance with applicable SOPs.

Instructions for the collection and handling of biological samples will be provided in the laboratory manual or by the sponsor. The actual date and time (24-hour clock time) of each sample will be recorded.

The actual times may change, but the number of samples will remain the same. Collection of samples within the protocol-allowed visit window, as defined in the SoA or above will not be captured as a protocol deviation, as long as the exact time of the collection is noted on the source document and the CRF.

Sample will be used to evaluate the PD of ponsegromab. Samples collected for PD analyses may also be used to evaluate safety or efficacy aspects related to concerns arising during or after the study, and/or evaluation of bioanalytical methods, or for other internal exploratory purposes.

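### Effect modification by screening GDF-15 is assessed only through a two-level split; one exploratory model that keeps GDF-15 continuous would use the data better

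*SAP*

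**What the plan says.** SAP 6.5 lists screening GDF-15 (Roche assay) as a subgroup factor for the primary endpoint, "dichotomized using < or ≥ overall study median level (or an alternative cut-point, if appropriate". The model is the body-weight MMRM of SAP 6.1.1.1, extended as follows: "Additional terms for the subgroup factor and its interaction with treatment group, time and the treatment-by-time interaction, will be included in the model". The least-squares means, differences from placebo and interaction p-values reported for GDF-15 therefore all rest on two groups. No criterion, candidate value or deadline is given for an alternative cut.

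The one continuous use against weight is graphical: "screening Roche GDF-15 will be plotted vs Week 12 change from baseline body weight using a scatterplot". The SAP says the plot "may be colored/trellised by different cancer types and/or type of therapy". It does not mention separating the randomized arms, a fitted line or an interaction estimate.

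The variable is not incidental. Protocol 2.2 states that "Ponsegromab is an anti-GDF-15 mAb". Inclusion criterion 4 requires "Serum GDF-15 concentrations of ≥1.5 ng/mL". On the screening sample, Protocol 8.7.1 adds that "this sample may be used to help support development of a potential companion diagnostic test for ponsegromab".

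**The concern.** A continuous baseline value, measured in everyone enrolled, is reduced to two levels in the only model that asks whether benefit depends on it. If benefit changes gradually with GDF-15, the split treats patients just above and far above the median as the same, and precision is lost. The scatterplot shows the raw values but yields no estimate. Without separation by arm it cannot distinguish a prognostic relation (weight change varies with GDF-15 in everyone) from effect modification (the difference from placebo varies with GDF-15).

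At stake is an exploratory question: how the treatment effect varies with GDF-15 within the enrolled range. The open wording on the cut-point adds a smaller problem. A reader of the results could not tell how a non-median cut had been reached.

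**Working it through.** **The plan's own figure.** Protocol 9.5 gives 30 completers per arm, 39 placebo participants' worth of prior information, SD 4.9 kg, a true difference of 2.7 kg and a 1-sided 5% test.

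- SE = 4.9 × √(1/30 + 1/69) = 1.07 kg.
- Power is 80.9% (normal) or 80.4% (t), against about 80% stated.
- The smallest significant difference is 1.76 to 1.78 kg, against 1.8 kg stated.

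These reproduce. The documents give no figure for the GDF-15 interaction.

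**Information kept by a split.** For an interaction linear in x, replacing x by a two-level indicator d keeps a fraction corr(x, d)² of the information. For normal x cut at its median:

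- covariance = 0.399 and var(d) = 0.25, so the fraction is 0.399² / 0.25 = 2/π = 0.637.
- Loss = 36.3%.
- 0.363 × 120 completers = 44. For one dose plus placebo, 0.363 × 60 = 22.

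**With the protocol's GDF-15 distribution.** Protocol 4.3 expects medians for NSCLC, PANC and CRC of "approximately 3.02, 3.32, and 3.50 ng/mL, respectively", 95th percentiles of 8.69, 9.35 and 13.4 ng/mL, and a 4:4:3 mix of NSCLC, CRC and PANC. A lognormal shape is assumed, with σ = ln(95th percentile / median) / 1.645, giving 0.643, 0.629 and 0.816.

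| Case (effect linear in log GDF-15) | Loss from median split |
|---|---|
| Single tumour type, truncated at 1.5 ng/mL | 34.2% to 36.1% |
| 4:4:3 mix, truncated at 1.5 ng/mL | 35.6% |
| 4:4:3 mix, not truncated | 37.3% |

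The range for single tumour types covers both readings of Protocol 4.3: that its percentiles describe patients before or after the entry threshold is applied.

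**Other shapes and cuts.** If the effect were linear in ng/mL, the loss would be about 54% to 71%. If it were a step exactly at the cut, there would be none. On the truncated mix with a log-linear effect, other cuts lose about 35% (67th percentile), 38% (75th), 55% (25th) and 57% (90th).

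**What this means for power.** Take one dose against placebo, with the median dividing each arm into 15 and 15 completers, and use the 1-sided 5% level of SAP 5.1 as a yardstick. The SAP sets no level for the interaction.

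| | Median split | Continuous log GDF-15 |
|---|---|---|
| SE of the difference in effect between halves | 4.9 × √(4/15) = 2.53 kg | 2.53 × √0.637 = 2.02 kg |
| 90% CI half-width (1.645 × SE) | 4.2 kg | 3.3 kg |
| Difference detectable with 80% power (2.486 × SE) | 6.3 kg | 5.0 kg |
| Power if the difference is 2.7 kg | 28% | 38% |

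Put another way, an interaction with 80% power when continuous would have about 63% after a median split (61% at 2-sided 5%). A simulation with 30 per arm, a normal covariate and t tests at 2-sided 5% gave 75% and 54%. Both are lower in small samples, with a similar gap.

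**The case against.** The strongest reply is that little depends on this analysis. It is one of three unadjusted subset analyses in a Phase 2 trial. SAP 5.1 does not list it among the formal tests, and the interim subset tables in SAP 7.2.1 are by tumour type only. A two-group display is also a natural form for a future threshold test. The continuous model does not rescue the question, since 38% power is still low, and it needs log-linear slopes for three doses at three visits in skewed data. All of this stands. It limits the point to a cheap improvement, but it gives no reason to omit the model.

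A second reply concerns the cut-point. A reader might infer that it will be picked after unblinding to make a subgroup look best. The documents do not say so. The median is the named default, and screening GDF-15 is a pre-treatment value that can be reviewed blind. SAP version 3 followed a blinded data review, and Protocol 9.3 requires the SAP to be final before any analysis. What remains is that the SAP states no rule or timing. By contrast, SAP 4 has prohibited procedures and medications settled by blinded review before database lock.

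It might also be said that the population PK/PD work (Protocol 9.3.5, SAP 6.6.6) covers the question. That work is optional and relates ponsegromab concentration to the endpoints. It does not commit to screening GDF-15 as a modifier.

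**Conclusion.** The point holds as a modest improvement to an exploratory analysis. If modification is roughly linear in log GDF-15, keeping GDF-15 continuous lowers the SE of the interaction by about 20% (1 − √0.637) at almost no cost. That shape is an assumption, and the documents do not state one.

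Two stronger readings should be resisted:

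- **That the trial loses a third of its information, or some 61 of 168 participants (0.363 × 168).** The loss applies to this interaction only and depends on the shape above. The relevant base is the planned completers. The primary Week 12 estimate and its power are untouched.
- **That the split undermines the enrichment strategy.** Everyone randomized is at or above 1.5 ng/mL, so no model of these data, split or continuous, can compare patients above and below the entry threshold. Protocol 4.2 sets that threshold from the healthy-subject distribution. Protocol 8.7.1 ties the possible diagnostic to no body-weight analysis.

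**What to change.** In SAP 6.5:

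1. Add one exploratory MMRM with log screening GDF-15 as a continuous covariate and its treatment, time and treatment-by-time interactions. Report Week 12 differences from placebo, with 90% intervals, at the quartiles of GDF-15.
2. Keep the median split for display.
3. Delete the alternative cut-point, or state its value or selection rule before unblinding.
4. Show the scatterplot by randomized arm, so that log-linearity can be checked within arms.
5. Correct the lead-in, which announces two subgroup factors before a list of three.

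The cost is one extra model on data already collected, and a log-linear assumption that the revised scatterplot can check. The report should say that power for this interaction is low under either coding.
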